8.8.2.2 Analysis of Intensive PD Samples

A descriptive summary will be provided for the FGF19, C4, and bile acid endpoints including measured concentrations, change from baseline, and percentage change from baseline using 8-number summary by visit, treatment group, and nominal time. For Days 1 and 84 (overlaid), linear plots of the arithmetic mean concentration (\pm SD) versus nominal sampling time figures will be created for FGF19, C4, and bile acid endpoints.

Change from baseline and the percentage change from baseline in the FGF19, C4, and bile acid concentrations for each nominal time by visit will be analysed using an ANCOVA model with treatment as fixed effect and the associated baseline value as covariate with the Week 12 visit being considered the primary visit of interest. Least squares means and standard errors will be presented for each visit, p-value and 2-sided 95% confidence interval for treatment differences will be presented for each visit. Significance tests will be based on least-squares means using a two-sided $\alpha = 0.05$.

The area under the curve from 0 to 8 hours (AUC_{0-8}) and from 2 to 8 hours (AUC_{2-8}) will be computed for FGF19 and C4 at Days 1 and 84 using the linear trapezoidal rule.

Descriptive summaries of AUC_{0-8} and AUC_{2-8} (sample size, arithmetic means, geometric means, standard deviation (SD), %CV, minimum, median, maximum, and %GCV) for FGF19 and C4 will be presented by visit and treatment group.

The change from baseline and percent change from baseline for AUC_{0-8} and AUC_{2-8} will be computed for Day 84 using the parameter value at Day 1 as the baseline value.

Change from baseline and the percentage change from baseline in the AUC_{0-8} and the AUC_{2-8} for FGF19 and C4 at Day 84 will be analysed using an ANCOVA model with treatment as fixed effect and the associated baseline value as covariate. Least squares means and standard errors will be presented for each visit, p-value and 2-sided 95% confidence interval for treatment differences will be presented for each visit. Significance tests will be based on least-squares means using a two-sided $\alpha = 0.05$.

A by-subject listing will be provided for observed and derived variables. Composite (i.e.

“spaghetti”) plots of individual subject FGF19, C4, and bile acid concentrations versus time will be created on the linear scale.

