7.1.3. Baseline (Day 1)

Subjects who meet all inclusion criteria and none of the exclusion criteria will report to the clinic on the morning of Study Day 1 after fasting overnight for a minimum of 8 hours. After a review of applicable inclusion and exclusion criteria, subjects who continue to satisfy eligibility

requirements will be randomized in a 2:2:1 ratio to their treatment group. Predose assessments and procedures will be conducted as noted in the SoA (Table 19) and considered Baseline values.

After predose study procedures are completed, subjects will receive the first dose of study drug in the clinic on Day 1 followed by PK and biomarker blood draws. [REDACTED]

[REDACTED] K and PD samples will be collected as described in SoA (Table 19).

Before leaving the clinic, subjects will receive study medication and instructions on how to take the medication at home.

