3.2 Randomization and blinding

3.2.1 Randomization

Subjects will be randomized to study treatment using an Interactive Web Response System (IWRS). Subjects will be stratified initially by prior liver biopsy vs no prior liver biopsy. Subjects will be randomized to the treatment groups shown below:

- Treatment Group 1 (N=50); EDP-305 1 mg orally for 12 weeks
- Treatment Group 2 (N=50); EDP-305 2.5 mg orally for 12 weeks

- Treatment Group 3 (N=25); Placebo (PBO) orally for 12 weeks

A minimum of 10 subjects per treatment group will be included in the PK/PD substudy. The randomization code will be produced by Enanta (or designee). The Enanta unblinded biostatistician or designee will review and approve the final randomization list.

During the Screening period, subjects will be identified by a unique screening number assigned by the clinical site. Subjects who have completed screening assessments and are eligible for participation in the study will be randomized before the first dose of study drug (Day -1 or Day 1) and assigned a unique subject number which will be used to identify the subject throughout the study.

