3.3 Study treatments and assessments

The maximum study duration from Screening period to end of the safety follow-up period is 20 weeks. The duration of treatment is 12 weeks.

EDP-305 will be supplied as 1 mg and 2.5 mg tablets for oral administration; doses administered will be 1 mg, 2.5 mg or placebo taken once daily (QD) for 12 weeks.

The subject will be instructed to take all study drug doses at home except when study drug will be administered in the clinic (i.e., at the Days 1 and 3, and Weeks 2, 4, 8 and 12 visits). The subject will be instructed to take the study drug approximately at the same time every day (i.e., orally in the morning after fasting overnight for a minimum of 8 hours). If a subject forgets to take their study drug at their scheduled time, the dose may be taken later that day following a minimum of 4 hours fast; however, no more than 1 dose should be taken on any calendar day and a minimum of 16 hours between doses should be maintained.

A detailed description of procedures and assessments to be conducted during this study is summarized in the Scheduled of Study Assessments in the table below.

Table 2: Schedule of Study Assessments

Study Event	Screening ¹	Study Assessments per Planned Study Day						EOS
Visit Day	D-28 to -1	D1 ²	D3	D14±2	D28±2	D56±2	D84±3 ³	D112±2
Treatment Week⁴				W2	W4	W8	W12/EOT ⁵	W16
ICF ⁶ ; Demography; Medical History	x							
Inclusion/Exclusion	x							
FSH ⁷ ; HIV, HCV, and HBV	x							
Pregnancy Test ⁸	x	x			x	x	x	x
Height, Weight and BMI ⁹	x	x					x	x
Physical Exam ¹⁰	x	x	x	x	x	x	x	x
Vital Signs ¹¹	x	x	x	x	x	x	x	x
Oral Temperature	x	x						x
ECG	x	x	x		x		x	
Waist to Hip Ratio		x					x	
Safety Lab. Tests ¹²	x	x	x	x	x	x	x	x
PT/PTT and INR	x							x
CV Markers ¹³		x		x	x	x	x	x
MRI-PDFF, MRE	x						x	
ELF Panel, PRO C3, Inflammatory Markers ^{14, 15}		x					x	
APRI, FIB-4, and NFS		x					x	
FGF-19, C4, BA, and ALT ¹⁶		x		x	x	x	x	
PK/PD sub study (PK, C4, FGF-19, BA, and ALT) ¹⁷		x		x	x	x	x	
Population PK samples ¹⁸		x		x	x	x	x	
CK-18 and GLP-1 ¹⁵		x		x	x	x	x	
Study Drug Dosing ¹⁹		Daily Dosing						
Drug Accountability			x	x	x	x	x	
AE/SAE & Con Meds	x	x	x	x	x	x	x	x
Exploratory research samples ¹⁵		x			x	x	x	

1. Screening assessments should be conducted within 28 days prior to the first dose of study drug (i.e., Study Days -28 to -1)

2. On Day 1, all samples are to be collected predose with the exception of post dose PK and PD samples

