7 STATISTICAL CONSIDERATIONS AND ANALYSIS

7.1 Derived variables

The below table provides the list of derived variables for demographic and baseline characteristics, various duration derivations, drug compliance, baseline derivations and other important derivations applicable for this study.

Table 3.

Variables	Formula
Demographic and Baseline characteristics	
Age at informed consent (in years)	floor ((date of informed consent – date of birth + 1)/ 365.25)
Body mass index (BMI) (kg/m ²)	weight (kg) / [height (m)] ²
Derivation of Duration	
Study day at any visit	Date of interest – date of first dose of study drug. One day is added if this difference is ≥ 0
Extent of Exposure (Days)	Date of last randomized study drug intake – Date of first randomized study medication intake + 1
Extent of Exposure (Weeks)	Extent of exposure (days)/7
Drug Compliance	
Compliance	$100 \times [1 - (\text{Number of days of study drug interruption}) / (\text{Extent of exposure (days)})]$
Baseline Derivations	
Baseline (Average)	The average of the screening and the day 1 values.
Baseline (Last value pre-dose)	Last non-missing values collected prior to the first dose of study drug
Screening	The value obtained at screening.
Change from Baseline	Post Baseline value – Baseline
Percentage change from Baseline	$[(\text{Change from Baseline}) / \text{Baseline}] * 100$
Other Derivations	
Creatinine Clearance (Cockcroft-Gault)	$CL_{Cr} (\text{mL/min}) = \{((140 - \text{age [years]}) \times \text{weight}) / (72 \times S_{Cr})\} \times 0.85$ (if female). S_{Cr} = serum creatinine
AST to Platelet Ratio Index (APRI)	$APRI = ([\text{AST (IU/L)} / \text{AST ULN (IU/L)}] / [\text{Platelets}(10^9/\text{L})]) \times 100$

	ULN = upper limit of normal
Fibrosis-4 score (FIB-4)	$FIB-4 = [Age \text{ (years)} \times AST \text{ (IU/L)}] / [Platelets \text{ (} 10^9/L) \times (\sqrt{ALT \text{ (IU/L)}})]$
NAFLD fibrosis score (NFS)	$NFS = -1.675 + 0.037 \times Age \text{ (years)} + 0.094 \times BMI \text{ (kg/m}^2) + 1.13 \times IFG/Diabetes \text{ (yes = 1, no = 0)} + 0.99 \times AST/ALT \text{ ratio} - 0.013 \times Platelets \text{ (} 10^9/L) - 0.66 \times Albumin \text{ (g/dL)}$

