8.8 Pharmacokinetics (PK) and Pharmacokinetics/Pharmacodynamics (PK/PD) Analysis

During the study, PK samples and PD samples for FGF19, C4, bile acid, and ALT will be collected according to one of two schedules on Days 1 and 84. Subjects agreeing to participate in the PK/PD substudy will have samples collected at four discrete times: predose and 2, 6, and 8 hours after administration of EDP-305 on Days 1 and 84. This scheme will be referred to as “intensive” sampling in this SAP. On Days 1 and 84, all other subjects will have a sample collected predose, a second sample collected 1 to 3 hours after administration of EDP-305, and a third sample collected at least 1 hour after the second sample. This scheme will be referred to as “sparse” sampling. Additionally, all subjects will have PK, FGF19, C4, bile acid, and ALT samples collected according to the sparse scheme on Weeks 2, 4, and 8.

For the sparse sampling scheme, the nominal window for the first post-dose sample is defined relative to the time of EDP-305 administration while the nominal window for the second post-dose sample is defined relative to the time of collection of the first post-dose sample. As a consequence, actual sampling times for the second post-dose sample may fall within the 1- to 3-hour window described for the first post-dose sample. For example, if the first post-dose sample is collected 1 hour after EDP-305 administration and the second post-dose sample is collected 1 hour later, then the both samples would fall within the 1- to 3-hour window. In addition, actual sampling times relative to EDP-305 administration for post-dose samples collected according to the sparse scheme may vary between subjects and study visits. To permit more meaningful summarization, post-dose samples collected according to the sparse scheme will be binned by actual elapsed time since the time of the reference dose of EDP-305 for each visit. Bins for sparse post-dose samples are described in Table 3. Bins may be modified based on the distribution of the data.

Table 3: Bin Time for Post-Dose Sparse Samples

Bin Time Midpoint (hr)	Range for actual post-dose sample time (relative to time of EDP-305 dose)
0.5	0 to < 1 h
2.0	≥ 1 to < 3 h

4.0	≥ 3 to < 5 h
6.0	≥ 5 to < 7 h
8.0	≥ 7 to < 9 h

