8.8.2.3 PK/PD Analysis at Week 12 for Subjects with Intensive Samples

Correlation and PK/PD plots will be created using all subjects in the PK population. Correlation and other PD plots will be created using all subjects in the efficacy population, including placebo, as applicable. The following scatterplots will be generated:

- AUC_{0-8} in FGF19 with EDP-305 AUC_{last} for Day 1 and Day 84 (Week 12)
- AUC_{2-8} in FGF19 with EDP-305 AUC_{last} for Day 1 and Day 84 (Week 12)
- AUC_{0-8} in C4 with EDP-305 AUC_{last} for (Day 1 and Day 84 [Week 12])
- AUC_{2-8} in C4 with EDP-305 AUC_{last} for (Day 1 and Day 84 [Week 12])
- Percentage change from Baseline in AUC_{0-8} FGF19 with EDP-305 AUC_{last} (Week 12)
- Percentage change from Baseline in AUC_{2-8} FGF19 with EDP-305 AUC_{last} (Week 12)
- Percentage change from Baseline in AUC_{0-8} C4 with EDP-305 AUC_{last} (Week 12)
- Percentage change from Baseline in AUC_{2-8} C4 with EDP-305 AUC_{last} (Week 12)
- Percentage change from Baseline in Bile Acid (predose) with EDP-305 AUC_{last} (Week 12)
- Percentage change from Baseline in ALT (predose Week 12) with percentage change from Baseline in AUC_{0-8} FGF19 (Week 12)
- Percentage change from Baseline in ALT (predose Week 12) with percentage change from Baseline in AUC_{2-8} FGF19 (Week 12)
- Percentage change from Baseline in ALT (predose Week 12) with percentage change from Baseline in AUC_{0-8} C4 (Week 12)
- Percentage change from Baseline in ALT (predose Week 12) with percentage change from Baseline in AUC_{2-8} C4 (Week 12)
- Percentage change from Baseline in ALT (predose Week 12) with EDP-305 AUC_{last} (Week 12)
- Percentage change from Baseline in FGF19 (predose) with EDP-305 C_{max} (Week 12)
- Percentage change from Baseline in C4 (predose) with EDP-305 C_{max} (Week 12)
- Percentage change from Baseline in Bile Acid (predose) with EDP-305 C_{max} (Week 12)

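### The Day 84 FGF19 and C4 AUC tests take a mostly or wholly post-dose Day 1 AUC as baseline, so they misstate the drug effect if the first dose already acts

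*SAP*

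**What the plan says.** Substudy subjects give samples "predose and 2, 6, and 8 hours after administration of EDP-305 on Days 1 and 84" (SAP 8.8). From these, SAP 8.8.2.2 derives AUC0-8 and AUC2-8 of FGF19 and C4 on both days by the linear trapezoidal rule. Change and percentage change in these AUCs "will be computed for Day 84 using the parameter value at Day 1 as the baseline value". The model for these changes reads: "for FGF19 and C4 at Day 84 will be analysed using an ANCOVA model with treatment as fixed effect and the associated baseline value". The Day 1 AUC is therefore the covariate, and the output includes p-values and confidence intervals for treatment differences. Placebo is included (SAP 8.8.2).

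Every general baseline rule is predose. Protocol 7.1.3 has "Predose assessments and procedures will be conducted as noted in the SoA (Table 19) and considered Baseline values", and one of the definitions in SAP Table 3 is "Last non-missing values collected prior to the first dose of study drug". Note 2 to the SAP's schedule of assessments makes the exception visible: "On Day 1, all samples are to be collected predose with the exception of post dose PK and PD samples".

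On substudy size, SAP 3.2.1 states: "A minimum of 10 subjects per treatment group will be included in the PK/PD substudy". FGF19, C4 and bile acid at Week 12 are secondary endpoints (SAP 4.2).

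**The concern.** A baseline covariate should be something that treatment cannot have changed. The Day 1 AUC is measured after randomisation and mostly or wholly after the first dose. If EDP-305 moves FGF19 or C4 within 8 hours, part of the drug effect sits in the covariate and is adjusted away. In the percentage-change analysis it also sits in the denominator. SAP 8.8.2.3 plots these same Day 1 AUCs against Day 1 EDP-305 exposure, so the plan itself allows that they may respond to the drug.

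FGF19 and C4 are the FXR activity markers in a dose-ranging study. If the two doses differ in their first-dose effect, the distortion differs by dose, and the dose comparison on the integrated profile is affected too. The percentage-change AUCs also feed scatterplots in SAP 8.8.2.3 and the C4 and pruritus summaries in SAP 9.

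**Working it through.** The plan gives no power or effect figure for this analysis. Its only power figure (80.438%) is for ALT and does not bear on it.

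**1. How much of the baseline is post-dose.** With samples at 0, 2, 6 and 8 h, the trapezoids give:
- AUC0-8 = (C0 + C2) + 2(C2 + C6) + (C6 + C8) = C0 + 3C2 + 3C6 + C8. The post-dose weight is 7/8 = 87.5%.
- AUC2-8 = 2C2 + 3C6 + C8. The post-dose weight is 100%.

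**2. Absolute change.** Regressing (Day 84 − Day 1) on treatment and Day 1 gives the same treatment coefficient as regressing Day 84 on treatment and Day 1. That coefficient is D84 − b × D1, where D1 and D84 are the drug-minus-placebo differences in AUC and b is the within-arm slope. D1 and b are not in the documents, so the values below are assumptions. With D84 = 1:

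| D1 | b = 0.3 | b = 0.5 | b = 0.7 |
|---|---|---|---|
| 0 | 1.00 | 1.00 | 1.00 |
| 0.5 | 0.85 | 0.75 | 0.65 |
| 1 | 0.70 | 0.50 | 0.30 |
| 1.5 | 0.55 | 0.25 | −0.05 |
| −0.5 | 1.15 | 1.25 | 1.35 |

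Large-sample simulation agreed with the formula to within about 0.015. The estimate shrinks when b > 0 and Day 1 moves the same way as Day 84, and its sign reverses once b × D1 exceeds D84. It moves away from zero if Day 1 moves the opposite way, or if b < 0 (D1 = 0.5, b = −0.3 gives 1.15).

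**3. Percentage change.** The formula does not carry over, because the Day 1 AUC is also the divisor. Assume lognormal AUCs with a CV of 30%. Each cell gives the ANCOVA estimate in percentage points with the Day 1 AUC as baseline, then with a baseline free of drug effect, then the ratio of the two:

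| Within-arm correlation | Fall: Day 1 ×0.6, Day 84 ×0.4 | Rise: Day 1 ×1.5, Day 84 ×2 |
|---|---|---|
| 0 | −77.6 vs −65.4 (119%) | 82.4 vs 108.9 (76%) |
| 0.5 | −55.0 vs −62.7 (88%) | 57.3 vs 104.3 (55%) |
| 0.8 | −41.9 vs −61.1 (69%) | 42.8 vs 101.7 (42%) |

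So zero correlation does not remove the bias, and a falling marker can be pushed away from zero. With CV 30% to 50% and zero correlation, a 50% fall with a Day 1 effect half as large keeps 105% to 111% of its size. A 100% rise keeps 48% to 76% when the Day 1 effect is half to all of the Day 84 effect. With no Day 1 effect, the two baselines agree.

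**4. What it could do in the substudy.** Simulated trials with 10 per arm, an assumed Day 84 difference of 1.5 SD, b = 0.5 and absolute change:
- Day 1 AUC as covariate: power of about 95%, 75% and 34% when D1/D84 is 0, 0.5 and 1.
- Predose covariate with correlation 0.5: power of about 96%.

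**5. Precision cost of a predose covariate.** With 10 per arm, the SE of a drug-placebo difference is √[(1 − r²) × 2/10] in SD units. This is 0.27 at r = 0.8, 0.39 at r = 0.5 and 0.43 at r = 0.3.

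**6. Secondary note.** Two other analyses condition on Week 12 outcomes. SAP 8.6.3.1 repeats an ANCOVA with Week 12 liver-fat response as a fixed effect, and it is unclear whether the outcome is ALT or liver fat. SAP 8.6.4.2 lists Week 12 MRE, MRI-PDFF and ALT-change categories as potential exploratory subgroups. If ALT change were compared within ALT-change bands, the SAP 5 assumptions (−40 vs −10, SD 40, normal) would turn the −30 difference into about −0.16 in each 10-unit band.

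**The case against.** The strongest reply is that SAP 8.8.2.2 sets this baseline deliberately and no predose AUC exists to replace it. That stands. A reader might infer that the SAP contradicts its own baseline definition, but an explicit exception is not a contradiction.

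Second, nothing shows that the first dose acts by 8 hours. The Phase 1 results and the dose justification are redacted, and planning a scatterplot does not establish a response. That also stands: without a Day 1 effect there is no bias. But a prespecified test should not depend on the first dose being inert.

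Third, a reader might infer that these are the only formal drug-versus-placebo tests of FGF19 and C4 after dosing. They are not. SAP 8.8.2.1 and 8.8.2.2 also run ANCOVAs at each time bin or nominal time, with Week 12 the visit of primary interest. Those are unaffected if their associated baseline is the predose value. Dosing is once daily, so 0 to 8 h is not the whole dosing interval either.

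Fourth, the Day 1 AUC may predict the Day 84 AUC better than one predose value does. With b = 0.8 and D1 a quarter of D84, the planned model has about 99% power, against about 96% for a predose covariate with correlation 0.5. The precision point is fair, but the planned estimate would still be only 1 − 0.8 × 0.25 = 80% of the Day 84 effect.

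**Conclusion.** The point holds, as a minor one. The planned AUC model does not estimate the Day 84 drug-versus-placebo effect unless Day 1 shows no drug effect or, for absolute change only, b = 0. Its size cannot be taken from the documents; the figures above rest on assumed D1, b, CV and correlation.

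A reader might infer that the tests always understate the effect. The documents do not support that: the direction depends on the sign and size of D1 and b and, for percentage change, on the correlation and on whether the marker rises or falls.

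Affected are the formal tests of change and percentage change in FGF19 and C4 AUC in the substudy, the percentage-change AUC plots in SAP 8.8.2.3, and the C4 AUC change outputs in SAP 9. Not affected are the Day 84 AUC summaries by arm (which carry no test), the per-time-point PD models (given a predose baseline) and the primary ALT analysis.

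**What to change.** - In SAP 8.8.2.2, compare Day 84 AUC0-8 and AUC2-8 between arms by ANCOVA with the Day 1 predose concentration of the same marker as covariate.
- If a percentage is wanted, model log Day 84 AUC with log predose concentration, report the back-transformed drug/placebo ratio, and add a rule for values below quantification.
- Keep Day 84 versus Day 1 AUC as a descriptive summary labelled *change since first dose*, without p-values, and relabel the matching outputs in SAP 8.8.2.3 and SAP 9.
- State in SAP 8.8.2.1 and 8.8.2.2 that the associated baseline for concentrations is the Day 1 predose value.
- Secondary: present the SAP 8.6.3.1 model with liver-fat response, and the Week 12 response and ALT-change subgroups in SAP 8.6.4.2, as descriptive associations without drug-versus-placebo p-values.

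The cost is SAP wording, since the predose sample is already collected. The downside is some loss of precision if the predose value predicts the Day 84 AUC less well. For example, the SE rises from 0.27 to 0.39 SD with 10 per arm if the correlation drops from 0.8 to 0.5.

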8.8.2.3 PK/PD Analysis at Week 12 for Subjects with Intensive Samples

Correlation and PK/PD plots will be created using all subjects in the PK population. Correlation and other PD plots will be created using all subjects in the efficacy population, including placebo, as applicable. The following scatterplots will be generated:

- AUC_{0-8} in FGF19 with EDP-305 AUC_{last} for Day 1 and Day 84 (Week 12)
- AUC_{2-8} in FGF19 with EDP-305 AUC_{last} for Day 1 and Day 84 (Week 12)
- AUC_{0-8} in C4 with EDP-305 AUC_{last} for (Day 1 and Day 84 [Week 12])
- AUC_{2-8} in C4 with EDP-305 AUC_{last} for (Day 1 and Day 84 [Week 12])
- Percentage change from Baseline in AUC_{0-8} FGF19 with EDP-305 AUC_{last} (Week 12)
- Percentage change from Baseline in AUC_{2-8} FGF19 with EDP-305 AUC_{last} (Week 12)
- Percentage change from Baseline in AUC_{0-8} C4 with EDP-305 AUC_{last} (Week 12)
- Percentage change from Baseline in AUC_{2-8} C4 with EDP-305 AUC_{last} (Week 12)
- Percentage change from Baseline in Bile Acid (predose) with EDP-305 AUC_{last} (Week 12)
- Percentage change from Baseline in ALT (predose Week 12) with percentage change from Baseline in AUC_{0-8} FGF19 (Week 12)
- Percentage change from Baseline in ALT (predose Week 12) with percentage change from Baseline in AUC_{2-8} FGF19 (Week 12)
- Percentage change from Baseline in ALT (predose Week 12) with percentage change from Baseline in AUC_{0-8} C4 (Week 12)
- Percentage change from Baseline in ALT (predose Week 12) with percentage change from Baseline in AUC_{2-8} C4 (Week 12)
- Percentage change from Baseline in ALT (predose Week 12) with EDP-305 AUC_{last} (Week 12)
- Percentage change from Baseline in FGF19 (predose) with EDP-305 C_{max} (Week 12)
- Percentage change from Baseline in C4 (predose) with EDP-305 C_{max} (Week 12)
- Percentage change from Baseline in Bile Acid (predose) with EDP-305 C_{max} (Week 12)

